7.4.4 Safety Analysis

All subjects entered into the study will have detailed information collected on adverse events throughout the study duration, and this information will be used for the overall study safety analysis. These factors will include: worsening of symptoms, development of new psychiatric symptoms, medical effects (syncope, seizure, or other), and any equipment failures.

7.5 Subject Population(s) for Analysis

All data collected from enrolled subjects, who meet the eligibility criteria and complete, at minimum, baseline assessments will be analyzed. In the event that a subject does not complete the full study, their completed time-points may still be used in analyses, such as characterizing baseline fMRI activity and symptom severity. Any subjects enrolled into the study and meeting the eligibility criteria, regardless of whether they received investigational product, may be included in these analyses.

8 Safety and Adverse Events

8.1 Definitions

8.1.1 Adverse Event

An **adverse event** (AE) is any symptom, sign, illness or experience that the Principal Investigator determines as significantly worse during course of the study. Intercurrent illnesses or injuries should be regarded as adverse events. Abnormal results of diagnostic procedures are considered to be adverse events if the abnormality:

- results in study withdrawal
- is associated with a serious adverse event

CONFIDENTIAL

- is associated with clinical signs or symptoms
- leads to additional treatment or to further diagnostic tests
- is considered by the investigator to be of clinical significance

For FDA regulated studies the FDA defines an adverse event as the following:

Adverse event means any untoward medical occurrence associated with the use if a drug in humans whether or not considered drug related.

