3.1.2 Study Intervention Phase

Allocation to Interventional Group - Subjects will be randomly assigned to receive TMS at either the fMRIguided target or the DLPFC during this study. This is a single-blind study, so the researchers will know the site of administration for each subject, whereas subjects will remain blinded. The research team will be responsible for randomizing subjects using a computer-based randomization algorithm.

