8.4.3 Investigator Reporting: Notifying the Penn IRB

In compliance with the University of Pennsylvania reporting requirements and timelines, the principle investigator ([name]) will submit reports within 10 working days of discovery (with one exception) for events that meet reporting criteria. If the adverse event involved a death and indicates that participants or others are at increased risk of harm, the investigator will submit a report to the IRB within 3 days. In the event that the investigator does not have enough information to complete the Reportable Event form within this timeframe, he will still submit a Reportable Event Form. In such cases, a follow up report will be provided once additional information has been obtained.

8.4.4 Sponsor reporting: Notifying the FDA (applies only to Penn sponsor –investigator IND/IDE holders)

To be determined.

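### Section 8.1.1 makes a symptom an adverse event only if the investigator judges it significantly worse, gives no criterion, and leaves open whether the broader definition it also quotes applies

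*Combined protocol and SAP*

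**What the plan says.** Section 8.1.1 defines an adverse event in four steps.

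- The opening sentence says that it "is any symptom, sign, illness or experience that the Principal Investigator determines as significantly worse during course of the study". No criterion for the judgement follows.
- The next sentence adds a category without that test: "Intercurrent illnesses or injuries should be regarded as adverse events".
- Diagnostic findings are then brought in conditionally: "Abnormal results of diagnostic procedures are considered to be adverse events if the abnormality" meets any one of five listed conditions. Only one of the five rests on the investigator's view of clinical significance.
- Last comes a second definition, introduced by "For FDA regulated studies the FDA defines an adverse event as the following". It reads: "Adverse event means any untoward medical occurrence associated with the use if a drug in humans whether or not considered drug related". It has no severity threshold and needs no investigator determination.

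The section does not say whether this study falls under the last definition. Section 8.4.4, on sponsor notification of the FDA, reads only "To be determined".

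Three sections depend on 8.1.1. Section 8.1.2 defines a serious event as a kind of adverse event. Section 8.2 commits to recording every adverse event in the study period. Section 7.4.4 says that "All subjects entered into the study will have detailed information collected on adverse events throughout the study duration" and bases the overall safety analysis on that information. It names symptom worsening, newly developing psychiatric symptoms, medical effects of any kind and device failures.

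**The concern.** Usual practice is to record every untoward event and then grade it. The opening sentence of 8.1.1 reverses this for symptoms, signs and experiences: a severity judgement decides whether an event exists at all. The judgement has no stated threshold, so two assessors following the protocol could record different events from the same patient. Anyone who used the quoted FDA wording would record a third, larger set.

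What is at stake is the completeness of the safety and tolerability data. The side effect that section 11.1 calls common is by its own description mild, which is the kind of event that a test of significant worsening removes. Safety and tolerability are also weighed at the interim look in 7.4.3. There is no DSMB (8.5.2), and 8.5.1 gives the principal investigator front-line responsibility for identifying events, so no independent board stands behind that discretion. No efficacy analysis is affected.

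**Working it through.** The plan gives no figure on this point to reproduce. The check is a comparison of sections, followed by one illustration.

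**Step 1: what passes the definition in 8.1.1.**

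| Kind of event | Opening definition and its additions | Quoted FDA definition |
|---|---|---|
| Intercurrent illness or injury | Counts | Counts |
| Abnormal diagnostic result | Counts if any of five conditions is met | Counts if untoward |
| Symptom, sign or experience, significantly worse in the investigator's view | Counts | Counts |
| Symptom, sign or experience, mild or new, not judged significantly worse | Does not count | Counts |

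The last row is the gap. It is narrower than the whole of safety, but it holds the mild effects that 11.1 describes: headache and a temporary effect on hearing. A new symptom could be read as worse than its absence at baseline, but it would still have to be judged significantly so.

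**Step 2: does a later section restore the missing row?** Section 8.2 records all adverse events, but an event that fails 8.1.1 is not one. Section 8.1.2 takes serious events from the same set. Section 7.4.4 analyses adverse event information, so it inherits the filter as well.

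**Step 3: does the definition fit the analysis?** Section 7.4.4 expects new psychiatric symptoms and medical effects beyond syncope and seizure, without a severity qualifier. Those categories are wider than the opening sentence of 8.1.1 admits.

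**Step 4: is severity handled elsewhere?** Section 8.3 classifies relatedness for each adverse event after it is recorded. Sections 8.1 to 8.4 have no matching step to grade the severity of events that are not serious. For symptoms, severity enters only as the entry condition.

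**Step 5: illustration.** Inputs: mild headache in about 25% of patients (11.1); 40 patients completing with usable data, out of 80 enrolled (4.5 and section 7). Let f be the share of these headaches that the investigator would call significantly worse. The documents do not give f, so it is an assumption ranging from 0 to 1.

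- Expected headaches among completers = 0.25 × 40 = 10.
- Counted under the opening sentence = 10 × f: 0 at f = 0, 5 at f = 0.5, 10 at f = 1.
- Counted under any untoward medical occurrence = 10.

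If all 80 enrolled were treated, the expected number would be 0.25 × 80 = 20, with 0 to 20 counted. Section 7 expects a large share to fail screening, withdraw or give unusable data, so 20 is an upper figure. In both cases the range means only none to all. It shows which events are exposed, not how many would be lost.

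**The case against.** The strongest reply is that other provisions would catch these events. Section 8.4 commits to the IRB's definition of reportable events and to recording adverse reactions and subject complaints. Section 8.5 has patients report symptoms at each treatment visit, and 6.2.2 adds short assessments before and after each stimulation session. Section 10.1 triggers a staff review without using the test in 8.1.1. Section 7.4.4 lists its content broadly. All of this is correct, and it makes it likely that much of the raw information will exist. It does not change what counts as an adverse event for 7.4.4. The trigger in 10.1 also starts above a mild temporary headache, so it does not reach the example here.

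The reply is also right against several stronger readings that a reader might draw:

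- **That nothing counts without the investigator's judgement.** Illnesses, injuries and qualifying abnormal results count without the opening test.
- **That the two definitions flatly contradict each other.** The second is conditional on FDA regulation and worded for a drug. If it applies, the gap closes; if not, the two do not compete. The defect is that applicability is unstated.
- **That adverse events are the only safety outcome.** Section 3.2.3 labels symptom follow-up as the primary safety endpoint, and the Columbia suicide severity scale is collected under 6.6. Adverse event information is the stated basis of the 7.4.4 analysis, which is a narrower claim.
- **That the filter is applied unblinded and biases a comparison of targets.** Section 3.1.2 says "the researchers will know the site of administration for each subject", but 5.4 says that the administering clinician is blinded. The documents do not settle what the person judging events knows. Section 7.4.4 plans an overall safety analysis and no comparison by site.

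**Conclusion.** The point holds in limited form. The opening sentence of 8.1.1 is a stated rule, not a missing detail, and following it can leave mild or newly arising symptoms out of the recorded events on which 7.4.4 rests. The same section quotes a definition without this filter and does not say whether it governs.

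Undercounting is the plausible direction, but its size cannot be derived from the documents. The figure of about 10 expected headaches among 40 completers assumes that the 25% in 11.1 applies per patient to this study; how many would be recorded depends on an unknown judgement. The documents do not establish bias between the two targets. The change is worth making because it is specific and cheap and affects how the trial's tolerability is described.

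**What to change.** - In 8.1.1, state one governing definition for recording: any untoward medical occurrence, new or worsened, whether or not considered related to TMS. Remove the significance judgement from the entry condition, and either delete the quoted drug definition or say that it is superseded.
- Record severity as a separate field, graded after the event is entered, beside the relatedness classification that 8.3 already requires.
- Align 8.2 and 7.4.4 with this definition, so that the events recorded are the events analysed. Device failures without a medical consequence can stay a separate listed item.
- Optionally, tabulate events in 7.4.4 by the site being treated at onset, and reconcile 3.1.2 with 5.4 on who is blinded.

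The cost is one replaced definition, one extra field and slightly more event entries. No visits are added.

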8.1.2 Serious Adverse Event

Adverse events are classified as serious or non-serious. A serious adverse event is any AE that is:

- fatal
- life-threatening
- requires or prolongs hospital stay
- results in persistent or significant disability or incapacity
- a congenital anomaly or birth defect
- an important medical event

Important medical events are those that may not be immediately life threatening, but are clearly of major clinical significance. They may jeopardize the subject, and may require intervention to prevent one of the other serious outcomes noted above.

8.2 Recording of Adverse Events

The PI will monitor the study for any serious and adverse events. All serious events (SAE) will be reported to the IRB: a) Death: immediately b) Life-threating and all other SAEs within 7 calendar days. Should there be a serious event that occurs that increases the risks to the participants the study will be stopped, an investigation will be conducted, and a findings report will be generated before the study is resumed.

All adverse events occurring during the study period will be recorded. The clinical course of each event will be followed until resolution, stabilization, or until it has been determined that the study intervention or participation is not the cause. Serious adverse events that are still ongoing at the end of the study period will be followed up to determine the final outcome. Any serious adverse event that occurs after the study period and is considered to be possibly related to the study intervention or study participation will be recorded and reported immediately.

8.3 Relationship of AE to Study

The relationship of each adverse event to the study procedures will be characterized. The PI will determine the relationship of each adverse event to the study procedures and how that relationship will be classified (definitely related, probably related, possibly related, unlikely, or unrelated).

8.4 Reporting of Adverse Events, Adverse Device Effects and Unanticipated Problems

This study will comply with the Penn IRB definition of reportable events and reporting timelines. The investigators and the protocol sponsor will conform to the adverse event reporting timelines, formats and requirements of the various entities to which they are responsible. Additionally all other events (unanticipated problems, adverse reactions, unanticipated adverse device effects and subject complaints will be recorded and reported with respect to institutional and federal policies as described in the Penn Manual.

8.4.1 Follow-up report

If an SAE has not resolved at the time of the initial report and new information arises that changes the investigator's assessment of the event, a follow-up report including all relevant new or reassessed information (e.g., concomitant medication, medical history) will be submitted to the IRB. The investigator is responsible for ensuring that all SAE are followed until either resolved or stable.

8.4.2 Investigator reporting: notifying the study sponsor

Any study-related unanticipated problem posing risk to subjects or others, and any type of serious adverse event, will be reported to the study sponsor by telephone within 24 hours of the event. To report such events, a Serious Adverse Event (SAE) form will be completed by the investigator and faxed to the study sponsor within 24 hours. The investigator will keep a copy of this SAE form on file at the study site.

Within the following 48 hours, the investigator will provide further information on the serious adverse event or the unanticipated problem in the form of a written narrative. This should include a copy of the completed Serious Adverse Event form, and any other diagnostic information that will assist the understanding of the event. Significant new information on ongoing serious adverse events should be provided promptly to the study sponsor.

8.4.3 Investigator Reporting: Notifying the Penn IRB

In compliance with the University of Pennsylvania reporting requirements and timelines, the principle investigator ([name]) will submit reports within 10 working days of discovery (with one exception) for events that meet reporting criteria. If the adverse event involved a death and indicates that participants or others are at increased risk of harm, the investigator will submit a report to the IRB within 3 days. In the event that the investigator does not have enough information to complete the Reportable Event form within this timeframe, he will still submit a Reportable Event Form. In such cases, a follow up report will be provided once additional information has been obtained.

8.4.4 Sponsor reporting: Notifying the FDA (applies only to Penn sponsor –investigator IND/IDE holders)

To be determined.

8.5 Medical Monitoring

[name], a board certified physician, will review all questionable screens for MRI and TMS safety and will be physically present (or a reasonable medically trained stand-in) for every TMS session conducted on any participant who indicates greater than minimal risk for experiencing syncope or a seizure in response to TMS which are the primary medical risks for this procedure. It is the responsibility of the Principal Investigator to oversee the safety of the study in collaboration with [name] and other collaborating medical staff. This safety monitoring will include careful assessment and appropriate reporting of adverse events as noted above.

Participants will meet the clinician treating them at each TMS treatment visit where they also report on their current symptoms. During the 3 week break, we also call them to assess symptom changes. Substantial worsening of symptoms to the point of potential threat determined by the study physician ([name]) and Pl (licensed psychologist) will result in a threat assessment of the patient which, depending on the degree of worsening, will facilitate: brief de-escalation interventions, request for self-admit to nearest emergency room, request for family/friend accompaniment to ER, or a call to emergency services for patient pick up. The procedures are all done within walking distance of the Department of Emergency Medicine at Penn Medicine, which will be the first choice for emergency services if the patient is ambulatory and willing to accompany study staff to the hospital. The VA hospital is also within walking distance and will be the preferred ER for veteran participants.

If the patient endorses a significant worsening of symptoms that is abnormal for their typical illness course or puts them into a category of imminent risk for self-harm, their participation will be discontinued.

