3.1 General Design

TMS will be administered to either the fMRI-guided target or DLPFC in a randomized, single-blind design. 40 patients diagnosed with Post-Traumatic Stress Disorder (PTSD) or trauma induced Major Depressive Disorder (MDD) and symptoms of depression, as determined by meeting the DSM criteria for PTSD or MDD as a primary diagnosis and scoring ≥10 on the PHQ-9, will be recruited for this study. They will be otherwise healthy adults, aged 18-60, with PTSD or trauma induced MDD as primary diagnosis and without current diagnoses of significant, problematic substance use disorders or with present or past diagnoses of psychosis or bipolar illness. All subjects will receive active TMS, so there is no placebo or sham condition. However, the patients will be blinded as to whether their site of stimulation is based on the clinical standardized targeting method or our novel fMRI-guided targeting method. TMS is administered to one of these two sites over a two-week period, and then TMS will be administered to the other site over a subsequent two-week period following a three week wash out period. All subjects will receive TMS to both sites as a part of the study, but the order is randomized and counterbalanced. All participants will be recruited through the community via study advertisements and through the University of Pennsylvania and the VA. Subjects can express interest by contacting the study staff; in most cases, this will serve as the primary method for acquiring contact information. Physician referrals and the use of the Penn Data Analytics Center will also be incorporated as recruitment methods. Section 4.3 further elucidates all recruitment methods. Prior to any study visits, all subjects will be screened in a telephone interview with a trained member of the study staff or via a self-report screening survey. The first study session will consist of a consenting and extended screening visit. The information collected in this initial visit will determine if the subject meets all inclusion criteria. We will also demonstrate TMS to ensure the subject is comfortable with all study procedures. At the second study session, participants will undergo an MRI procedure for 60 minutes. This will be used to generate the TMS targets for the study. Subjects will then return every weekday (5 days per week, minimum of 4 days per week) over two weeks to receive the TMS treatment (10 sessions). These visits will last approximately 60 minutes each. The daily administration of TMS is a necessary component of the study, as it is consistent with the standard operating procedure for FDAapproved clinical TMS. During the 2 weeks of TMS treatment, subjects will undergo the many of the same clinical assessments used during the screening and baseline visits, in order to examine changes in symptoms. Subjects will then spend 3 weeks away from the study team; during the break, there will be two phone/survey visits used as a safety assessment. After this break, subjects will then return every weekday (5 days per week, minimum of 4 days per week) over two weeks to receive the TMS treatment (10 sessions) to the other site examined in the study. Upon completion of the study, scheduled phone and survey visits will take place every 4 weeks (+/-7 days) over the subsequent 6-month period to monitor continued stability of clinical improvement and/or remaining clinical symptoms. Overall, this study consists of 1 consent/screening visit, 1 MRI scan, 20 total visits for TMS treatment, and 8 phone visits.

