3.2.3 Primary Safety Endpoints

Study follow-up will be conducted monthly, over a 6-month period upon completion of the study in order to determine the duration and stability of clinical improvements. In addition, a clinical assessment will be conducted at the end of each 2-week administration of TMS to any changes in mood and/or symptoms across the study as it is completed.

4 Study Population and Duration of Participation

We plan to enroll 80 patients to obtain useable data from 40 patients diagnosed with PTSD or trauma induced MDD and symptoms of depression, as determined by meeting the DSM criteria for PTSD or trauma induced MDD and having a PHQ-9 score \geq 10, will be recruited for this study. Participants will be otherwise healthy, aged 18-60, without significant concomitant diagnoses.

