additional clinical and neurocognitive assessments and will last approximately 2 hours During these neurocognitive assessments, we may collect EEG and eyetracking data, as in the Baseline Visit.

We may use Neuroflow software for recording participants' heart rate during each TMS treatment session. NeuroFlow's software platform analyzes data from a commercially available, third-heart rate monitor. NeuroFlow follows strict HIPAA guidelines with respect to patient privacy and data security, both from a technical and administrative respective. Only de-identified data will be recorded using this platform, no identifiers will be entered on the platform.

Participants will have a 3 week break from TMS treatment between the first set of TMS sessions (i.e., Visit 2-11/Weeks 1 & 2) and the second set of TBS sessions (i.e., Visits 13-23/Weeks 6 & 7). During this time, participants will not be coming into the lab. However, participants will be scheduled for two phone/survey visits approximately one week, and two weeks (+/- 3 days) following Visit #11, in which clinical assessments will be completed.

Due to the nature of TMS treatment, daily visits are necessary. In the event a participant misses a session, the participant may complete two TMS treatment sessions on one day with ample time in between. In this case, the principal investigator will consider the timeline of missed sessions and evaluate how the missed sessions may be made up appropriately. If too many sessions are missed (as per PI discretion), the participant may be withdrawn from the study without their consent.

6.2.3 3 week break & Phone Calls

Participants will have a 3 week break from TMS treatment between the first set of TBS sessions (i.e., Visit 2-11/Weeks 1 & 2) and the second set of TBS sessions (i.e., Visits 13-22/Weeks 6 & 7). During this time, participants will not be coming into the lab. However, participants will be scheduled for two phone calls and Check-In surveys approximately one week (+/- 3 days) and two weeks (+/- 3 days) following Visit #11, in which clinical assessments will be completed.

6.2.4 Visits 13 - 22

Visits 13-22 are the second set of TMS treatment visits and will consist of identical procedures and will take the same amount of time as Visits 2-11, but stimulations occurring at the targeted site not used in the initial round of TMS treatments Please see sections 6.2.2 for further explanation on these visits.

6.2.5 6 Month Follow-Up: Phone Calls

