Upon completion of the study, scheduled phone and survey visits will take place every 4 weeks (+/- 7 days) over the subsequent 6-month period to monitor continued stability of clinical improvement and/or remaining clinical symptoms. Each phone and survey visit will include clinical assessments and will take approximately 30-60 minutes.

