6.3 Subject Withdrawal

Subjects may withdraw from the study at any time. They may also be discontinued from the study at the discretion of the Investigator for lack of adherence to intervention, study procedures, or visit schedule. The Investigator or the Sponsor (if applicable) may also withdraw subjects who violate the study plan or to protect the subject for reasons of safety or for administrative reasons. It will be documented whether or not each subject completes the study. No tapering procedure with TBS is necessary or required in the event that a subject withdraws from this study.

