6.5 Other Evaluations, Measures

During the course of the study, patients' symptoms will be evaluated in order to determine changes in symptoms across the study. Symptom scales are detailed below in the "Efficacy Evaluations" section.

6.6 *Efficacy Evaluations*

The following clinical assessments will be utilized at baseline, after the first 2-week period of TMS treatment, during the TMS treatment 3 week break, and after the second 2-week period of TMS treatment (the end of the study) to evaluate the efficacy of the TMS interventions in improving clinical symptoms:

- Patient Health Questionnaire (PHQ-9)
- PTSD Checklist for DSM-5 (PCL-5)
- Montgomery-Asberg Depression Scale (MADRS)
- Columbia Suicide Severity Rating Scale (CSSRS)
- Positive and Negative Affect Schedules (PANAS 20 item)
- World Health Organization Quality of Life (WHOQOL-BREF)
- Snaith-Hamilton Pleasure Scale (SHAPS)

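### The plan does not separate stopping TMS from leaving the study, so read literally an early stopper has no further scheduled symptom scale or monthly call

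*Combined protocol and SAP*

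**What the plan says.** Three rules let staff end a patient's involvement.

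- Section 8.5 is mandatory: worsening that is abnormal for the patient's illness course, or that "puts them into a category of imminent risk for self-harm, their participation will be discontinued".
- Section 6.2.2 is discretionary: if the investigator judges that too many sessions have been missed, "the participant may be withdrawn from the study without their consent".
- Section 6.3 is also discretionary: "They may also be discontinued from the study at the discretion of the Investigator for lack of adherence to intervention".

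All three are written as leaving the study or ending participation. None mentions stopping TMS alone. At exit, section 6.3 asks only for a record of whether the subject completed. Leaving a single component is described only for EEG (section 11.1).

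Later contacts are tied to milestones.

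- Break calls (6.2.3) come "approximately one week (+/- 3 days) and two weeks (+/- 3 days) following Visit #11, in which clinical assessments will be completed".
- The efficacy scales (6.6) and the clinical assessment in 3.2.3 come after each two-week round.
- For the monthly calls, section 3.1 has: "Upon completion of the study, scheduled phone and survey visits will take place every 4 weeks (+/-7 days) over the subsequent 6-month period". Section 6.2.5 says the same, and 3.2.3 has: "Study follow-up will be conducted monthly, over a 6-month period upon completion of the study". Section 1.1 is looser and times the monthly measures from the TMS treatments.

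Section 6.6 equates the end of round 2 with the end of the study, whereas the Study Summary counts the 6-month follow-up inside the study.

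**The concern.** A patient who stops before the end of round 2 may never reach the milestone from which the next contact is timed, and the stopping rules say that participation is over. The text therefore gives staff no scheduled symptom scale or monthly call for that patient.

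This matters because significant worsening is itself a reason for removal. Patients who do badly are more likely to lack the later scores. Section 7.4 needs those scores twice: in the primary Site x Time ANOVA, which compares pre-treatment with symptoms straight after each round, and in the exploratory comparison of pre-treatment with 6 months. If one site led to more removals for worsening, it would lose more of its worst results and the difference between sites would be blurred. In the 6-month analysis, maintenance of benefit could look too favourable.

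**Working it through.** **Calendar.** Section 6.2.3 puts round 1 in weeks 1 and 2 and round 2 in weeks 6 and 7. The break calls fall about one and two weeks after Visit 11, at weeks 3 and 4. The six monthly calls fall at week 7 + 4k for k = 1 to 6, which is weeks 11, 15, 19, 23, 27 and 31. As a check, 2 break calls + 6 monthly calls = 8, the number of phone visits in section 3.1. Adding the two end-of-round assessments gives 8 + 2 = 10 scheduled points after treatment starts.

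**Points lost if participation ends at the stop.**

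| Stop | Scheduled points lost | Weeks to last planned call |
|---|---|---|
| After session 5 of round 1 (week 1) | 1 + 2 + 1 + 6 = 10 | 31 - 1 = 30 |
| In the break (weeks 2 to 5) | (0 to 2) + 1 + 6 = 7 to 9 | 31 - 5 = 26 to 31 - 2 = 29 |
| After session 5 of round 2 (week 6) | 1 + 6 = 7 | 31 - 6 = 25 |

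For a stop in the break, Visit 11 has been reached, so any remaining break calls are lost only because participation has ended. The Study Summary speaks of 9 weeks of treatment visits and section 1.1 of about a month between rounds. Either would move the week numbers. The counts depend only on the order of contacts and do not change.

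**What each analysis loses.** A stop in round 1 leaves no post-round score for either site. A stop in the break or during round 2 leaves one for the first site only. None of these patients has a 6-month score. Assessments at attended sessions survive (6.2.2 schedules short ones before and after stimulation, scales not named), but nothing is scheduled after the last attended session.

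**Size of bias.** The documents give no rate of early stopping. The allowance of 80 enrolled for 40 usable (section 7) mixes screen failures, withdrawals and unusable data. By formula, if a fraction d of treated patients stops early and their mean 6-month change is poorer than the completers' mean c by δ, the all-treated mean is (1 - d)c + d(c - δ) = c - dδ, so completers overstate it by dδ. With purely assumed values, d = 0.05 and δ = 0.5 SD give 0.025 SD, and d = 0.20 and δ = 1.0 SD give 0.20 SD. If stoppers had done better than completers, the sign would reverse. No conclusion here rests on these values.

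**The case against.** The strongest reply is that the plan already covers much of this.

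- Section 7.4.4 promises adverse-event information on everyone entered, throughout the study, including worsening and new psychiatric symptoms.
- Section 8.2 follows each event to resolution, stabilization or a finding that the study is not the cause. Section 8.5 provides threat assessment and emergency referral. Under 10.1 the study physician telephones after any medical consequence worse than a mild temporary headache.
- Section 7.5 says that all data from eligible subjects with baseline assessments will be analyzed.
- Section 9.1 asks staff to seek permission for vital status at the end of the scheduled period even from those who revoke authorization, so contact after departure is not foreign to the plan.
- The rules in 6.2.2 and 6.3 are permissive, and people may leave for reasons unrelated to outcome.
- The 6-month analysis is exploratory, and it cannot isolate a site effect in patients who had both sites.

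All of this stands, and it rules out three stronger readings. A reader might infer that early stoppers are left without safety follow-up; 7.4.4, 8.2, 8.5 and 10.1 say otherwise. A reader might infer that the analysis is restricted to completers; 7.5 does not say so. A reader might infer that further calls are forbidden; the plan is only silent.

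What the reply does not supply is a scheduled symptom scale or contact after the stop. Section 7.5 can analyze only data that exist. The looser timing in 1.1 is background text, and 3.1, 3.2.3 and 6.2.5 all use completion.

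**Conclusion.** The concern holds in this form: as written, stopping TMS and leaving the study are the same event, and about 7 to 10 scheduled points are lost per early stopper. That count assumes a literal reading and the visit order in section 6. Because the one mandatory removal rule is triggered by worsening, the missing data depend on outcome, and they can reach the primary post-round comparison as well as the 6-month analysis. The documents do not support a figure for the bias, nor a firm direction once other reasons for leaving are mixed in. This is a change that should be made: it is inexpensive, and follow-up not collected at the time cannot be recovered at analysis.

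**What to change.** In 6.2.2, 6.3 and 8.5, distinguish *stops TMS* from *withdraws from the study*. Anyone who stops TMS early stays in follow-up unless they decline. At stopping they complete remotely the 6.6 scales not already taken that day, together with the primary-analysis scale (7.4 names the Hamilton scale, which 6.6 does not list). They are then contacted at the remaining scheduled times.

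In 6.2.2 and 6.2.3, time the break calls from *the actual or scheduled date of Visit 11*. In 3.1, 3.2.3 and 6.2.5, time the monthly calls from *the actual or scheduled end of round 2*.

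In 7.4, include these scores in the primary post-round analysis for the round in which TMS stopped. A round never started contributes no score for that site, so the model must accept patients with one round. Report the 6-month result for all treated patients beside completers, with the numbers exposed to one site and to both and the time since last TMS. Leave the clinical stopping criteria unchanged.

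Cost: the lost points plus one contact at stopping, so 7 + 1 = 8 to 10 + 1 = 11 contacts. At the 30 to 60 minutes that 6.2.5 gives for a call, that is 8 x 0.5 = 4 to 11 x 1 = 11 staff hours per early stopper. Section 6.2.2 already allows remote assessment.

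Downsides: some patients will refuse. The all-treated 6-month summary mixes exposure and time since last TMS: for the mid-round-1 stopper above, the last call is 30 weeks after TMS, against 31 - 7 = 24 weeks for a completer. Contact after a self-harm concern must be coordinated with clinical care.
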